1. BACKGROUND, RATIONALE AND OBJECTIVES

1.1 Background

Abdominal aortic aneurysm (AAA) is a major health issue and ruptured AAA a common cause of death in Europe and North America. In Sweden 700-1000 annual deaths are attributed to AAA. To prevent rupture, early detection and preventive surgical repair in selected individuals is recommended. AAA screening programs are already implemented in the UK, Sweden and the USA. Most screening detected AAAs are, however, small (diameter 30-54 mm) and are under surveillance until expansion to the threshold for elective surgical repair; i.e. diameter ≥55 mm for men and ≥50 mm for women. Presently approximately 15,000 men and women are being monitored for small AAAs in Sweden, of whom 70% eventually will require surgical repair. In 2015, ~1200 AAA repairs were performed in Sweden at a cost of ~30 million Euros (Swedvasc 2016). AAA repair is associated with significant mortality (1-5%), perioperative complications (up to 20%), cost (~25,000 Euros/patient) and need for life-long post-operative follow-up, imaging and repeat surgery (in ~20% of cases) (Mani 2009, Mani 2010, Mani 2013).

A key limitation of contemporary treatment strategies of AAA is the lack of therapy directed at small AAA (Wanhainen 2019). Although surgical repair is an effective treatment for large AAA, several large trials (Powell JT 2007, UKSAT 2002, Lederle 2002, Cao 2011) have shown that early surgery of small AAA does not reduce mortality. Given that AAA diameter is the strongest predictor for rupture and the natural course for AAA is continued expansion, a mean to reduce AAA growth rate would be highly beneficial. Commonly used cardiovascular drugs, such as anti-platelet drugs, statins, angiotensin converting enzyme inhibitors and beta-blockers have not been shown to slow AAA growth in cohort studies (Ferguson 2010, Twine 2011). Previous interventional trials with therapy directed at AAA growth reduction include antibiotics, mast cell inhibitors, beta-blockers, platelet inhibitors, and angiotensin converting enzyme blockers, with trials of stem cells and cyclosporine under way. These trials have all been either small, with negative results or had unacceptable side effects (Meijer 2013, Sillesen 2015, PATI 2002, Golledge 2017, Rughani 2012).

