1.2.2 Secondary objectives

To examine if metformin limits increase in; a) CT-assessed AAA volume; b) ultrasound assessed AAA diameter; c) improves health-related quality of life; d) reduces the need for surgery (diameter ≥55mm) or rupture; and e) represents a cost-effective treatment to reduce the need for AAA surgery.

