5.1 Study measurements

5.1.1 Clinical data

At the enrolment visit the patients will undergo a clinical examination which consists of; recording of demographic data (date of birth, sex and ethnicity), medical history and concomitant diseases, smoking status, heredity of AAA, current medication, recording of weight & height, heart rate & blood pressure, cardio-pulmonary status and general appearance.

At all points of contact with phone or visit at the clinic any AE and SAE are recorded, target dose of study drug is determined and compliance is asked for. Discontinuation (temporarily or permanent) of study medication ≥ 3 consecutive days will be recorded.

At visits medical events and any changes in smoking status will be noted and vital signs and weight is recorded. Compliance to study drug is noted and remaining tablets are counted. At completion visit and at 24 months, the above plus a physical examination is performed. Changes in current medication are recorded yearly.

At enrolment visit, at 24 months and completion quality of life will be recorded with EQ-5D and RAND -36, see appendix 1.

At enrolment blood samples will be taken for fP-Glc and P-Creatinine, analysed at accredited hospital laboratory. P-Creatinine will be tested for safety every 12 months. A 24 months S-B12 is controlled for possible metformin induced deficiency. In Uppsala and Malmö venous blood samples will be taken at baseline, 24 months and completion for scientific reasons.

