8.2.2 Secondary variables

Secondary efficacy variables are; 1) difference in log-transformed AAA-volume determined by CT at 24 and 60 months vs at baseline (Log-transformation is undertaken because AAA volumes appear to follow a right-skewed distribution based on in house data), 2) difference in AAA-diameter determined by US at 24 and 60 months vs at baseline, 3) difference in circulating inflammation and matrix remodelling biomarkers assessed by established assays, 4) difference in quality of life score at 24 and 60 months vs at baseline, 5) difference in need for AAA surgery and aneurysm rupture at 24 and 60 months and 6) cost effectiveness of metformin treatment 2 g daily to reduce need for prophylactic surgery of AAA.

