8.3 Statistical analysis

The primary efficacy end-point is the between groups difference in mean annual AAA growth over 60 months. AAA growth will be analysed using an analysis of covariance (ANCOVA) model where AAA growth at 60 months is the dependent variable and treatment group and baseline AAA is included as independent variables. The results will be presented as the estimated group difference with 95 % confidence intervals at 60 months.

Similar methods will be used to assess growth as log transformed CT-volume and ultrasound diameter. Analysis of other outcomes: 1) Laboratory data and perivascular adipose tissue are exploratory endpoints and will be reported with descriptive statistics and evaluated with appropriate inferential statistics, 2) Patient reported outcome (QoL questionnaires) will be analysed using non-parametric test (Wilcoxson rank-sum test), 3) Pre-defined clinical events,

such as AAA-repair, rupture and death, are expected to be few, and the presentations will use descriptive statistics, 4) Economic analysis: Will be performed adopting a health system perspective. The cost-effectiveness analysis will produce an incremental cost effectiveness ratio as an estimated cost per surgical procedure avoided.

Handling of missing values: The primary analyses will be performed among patients with a measured value at the specific time point. However, as the number of missing values might be substantial several sensitivity analyses of the primary analysis will be performed:

- Multiple imputation (with different assumptions)
 - Assume that drop-outs respond according to randomized group
 - Assume that drop-outs respond according to control group
- Fixed imputation depending on reason for drop-out
 - For clinical events, such as AAA-repair, rupture and death, impute worst possible value
 - For other events impute using a maximum likelihood function

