8.4 Sample size estimation

Based on in house data and original data from an Australian study of the relationship between metformin and AAA growth (Golledge 2017) it is conservatively estimated that metformin treatment will lead to a 30% reduction in annual AAA growth. This is regarded as a meaningful change which is likely to translate to an important reduction in requirement for AAA repair. MRI data from the Uppsala group show a mean growth rate of 3mm/year, SD 2.17. Thus needing 184 patients for 80% power at a 30% reduced growth rate. CT data will likely show 10-15% larger SD, adding a 30% dropout rate over five years we approximate a need to recruit 500 patients, 250 in each arm, for 80% power at 2-tailed α 0.05.

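### The planned cost per procedure avoided would largely count postponed repairs, because no horizon, discounting or extrapolation beyond 60 months is stated

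*Combined protocol and SAP*

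**What the plan says.** Objective (e) in section 1.2.2 asks whether metformin "represents a cost-effective treatment to reduce the need for AAA surgery". Section 8.2.2 turns this into item 6, "cost effectiveness of metformin treatment 2 g daily to reduce need for prophylactic surgery of AAA", with no time point. Item 5, just before it, does have time points: "difference in need for AAA surgery and aneurysm rupture at 24 and 60 months".

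Section 8.3 gives the whole economic method in two sentences: "Will be performed adopting a health system perspective", then "The cost-effectiveness analysis will produce an incremental cost effectiveness ratio as an estimated cost per surgical procedure avoided". There is no horizon, discount rate, extrapolation or interval, and no rule that separates a repair prevented from a repair put off.

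Three other places bear on the point:

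- Section 2.1 ends the study at 60 months, or earlier if the patient discontinues.
- Section 1.1 describes small aneurysms as going on growing, says of monitored patients "of whom 70% eventually will require surgical repair", and prices a repair at about 25,000 Euros.
- Section 8.4 states "MRI data from the Uppsala group show a mean growth rate of 3mm/year, SD 2.17" and assumes that metformin cuts growth by 30%.

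**The concern.** A drug that slows growth moves the date at which an aneurysm reaches the repair threshold. It does not remove that date unless growth stops or the patient dies first. With no extrapolation planned, the only repairs the trial can count are those done during follow-up. A repair that falls in month 61 or later on metformin, but before month 60 on standard care, would then enter the ratio as avoided, and its whole cost would be booked as a saving.

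This bears directly on objective (e). A ratio built this way would make metformin look better value than the data can show, and a reader of the trial report could not tell how much of the saving is only timing.

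**Working it through.** **Inputs from the documents.** Growth 3 mm/year, SD 2.17, and a 30% reduction (section 8.4). Repair thresholds 55 mm for men and 50 mm for women, and about 25,000 Euros per repair (section 1.1). Baseline 30–49 mm for men and 30–44 mm for women (section 3.1). Follow-up to 60 months (section 2.1).

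**Assumptions not in the documents.** Linear growth; repair when the threshold is reached; discount rate 3–5% per year; mortality 3–8% per year; for the simulation in step 4, male baselines spread evenly over 30–49 mm.

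**Step 1: reproduce the plan's figure.** The difference is 0.30 × 3 = 0.9 mm/year. Per arm, n = 2(1.960 + 0.842)² × 2.17² / 0.9² = 91.3, so 92, or 184 in total. This matches section 8.4, so the growth inputs are being read as the plan uses them. The plan gives no figure for repairs avoided or for delay.

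**Step 2: proportional effect.** Let T = (threshold − baseline)/growth be the time to threshold on standard care. If each patient's growth is multiplied by 0.7, the time on metformin is T/0.7. The arms differ at 60 months when T ≤ 5 and T/0.7 > 5, that is, 3.5 < T ≤ 5. The delay is T/0.7 − T, which runs from 3.5/0.7 − 3.5 = 1.5 years to 5/0.7 − 5 = 2.14 years, whatever the patient's own growth rate.

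At 3 mm/year the counted repairs come from baselines of 55 − 15 = 40 mm to just under 55 − 10.5 = 44.5 mm in men (35 to just under 39.5 mm in women). For men:

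| Baseline (mm) | Standard care (years to 55 mm) | Metformin (years to 55 mm) | Delay (years) | Counted as avoided at 60 months |
|---|---|---|---|---|
| 40 | 5.00 | 7.14 | 2.14 | yes |
| 42 | 4.33 | 6.19 | 1.86 | yes |
| 44 | 3.67 | 5.24 | 1.57 | yes |
| 45 | 3.33 | 4.76 | 1.43 | no |

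**Step 3: effect ends at month 60.** By year 5 the treated aneurysm has covered 3.5 years' worth of untreated growth. The rest takes T − 3.5 years, so the threshold is reached at 5 + T − 3.5 = T + 1.5. The delay is 1.5 years for every counted repair.

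**Step 4: uniform effect.** A cut of 0.9 mm/year in every patient gives the same mean effect. In simulated men with growth Normal(3, 2.17), the results for counted repairs, with the effect continuing, were:

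| Form of effect | Median delay (years) | Delay over 2.2 years | Delay over 5 years |
|---|---|---|---|
| Proportional (× 0.7) | 1.79 | none (maximum 2.14) | none |
| Uniform (− 0.9 mm/year) | 1.56 | about 25% | about 3% |

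**Step 5: death before the postponed repair.** The chance is 1 − exp(−mortality × delay). It runs from 1 − exp(−0.03 × 1.5) = 4.4% to 1 − exp(−0.08 × 2.14) = 15.7%.

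**Step 6: value of the delay.** Postponing 25,000 Euros by d years at rate r saves 25,000 × (1 − (1 + r)^−d). At 3% and 1.5 years this is 1,084 Euros; at 5% and 2.14 years it is 2,479 Euros. Adding the repairs that death prevents:

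- Low end: 0.044 × 25,000 + 0.956 × 1,084 = about 2,100 Euros.
- High end: 0.157 × 25,000 + 0.843 × 2,479 = about 6,000 Euros.

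Both are set against 25,000 Euros when the repair is counted as avoided.

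**The case against.** The strongest case on the other side is that the plan writes no 60-month rule. Section 8.2.2 attaches 24 and 60 months to surgery and rupture, not to cost-effectiveness, so the economic team might yet model a longer horizon. This stands as a matter of wording: 60 months is inferred from the end of follow-up and the absence of any extrapolation. It does not rescue the ratio, because nothing in the plan would let it separate deferral from avoidance.

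Four stronger readings are tempting, and the documents do not support them:

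- **That the repairs are only postponed.** Patients may be up to 80 at entry (section 3.1), and if 70% eventually need repair, about 30% never do. Some postponed repairs will never happen.
- **That the delay is at most about two years.** Section 8.4 gives a mean reduction and does not say that each patient's growth is multiplied by 0.7. Step 4 shows that the ceiling fails under a uniform cut.
- **That the denominator would be close to zero.** Section 8.3 does expect few repairs. Yet at 3 mm/year the simulation has about 48% of standard-care men reaching 55 mm by month 60, against 30% on metformin (proportional effect). The two expectations conflict, so instability cannot be asserted from the documents.
- **That the result must be a cost per QALY.** Objective (e) is framed around the need for surgery, and no section sets a QALY standard. A cost per QALY cut off at 60 months would also still book a repair due in month 65 as a full saving. EQ-5D is scheduled ("At enrolment visit, at 24 months and completion quality of life will be recorded with EQ-5D and RAND -36"), but it may be missing after repair: section 2.1 lists repair as an example of leaving the study, while section 4.2 asks patients whose study drug is stopped, including for aortic surgery, to remain.

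**Conclusion.** The point holds in this form: as written, the ratio would largely credit postponed repairs as avoided ones. On the protocol's growth figures, with a proportional 30% effect, the counted repairs are put off by 1.5 to 2.1 years, or by 1.5 years if the effect ends at month 60. Under a uniform cut the typical delay is similar, but some slow growers wait much longer. A minority, about 4 to 16% under the assumed mortality, would not happen at all.

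The saving per counted repair would then be roughly 2,100 to 6,000 Euros in place of 25,000. That range rests on discount and mortality rates that the documents do not give, and on linear growth; the direction does not depend on the exact values. This is a secondary objective and leaves the primary analysis untouched, but it changes what the trial can conclude on objective (e).

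**What to change.** In section 8.3, and in item 6 of section 8.2.2:

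1. State a 60-month horizon for the within-trial economic analysis.
2. Relabel the ratio *cost per repair deferred beyond 60 months*.
3. Report beside it the between-arm difference in mean repair-free time to 60 months, saying how death and early withdrawal are counted, with bootstrap intervals for incremental cost and incremental effect.
4. Allow a claim of procedures avoided only from a prespecified extrapolation beyond month 60 in which growth continues, death is included and later repair costs are discounted at a stated rate.
5. If wanted, add cost per QALY from EQ-5D as a supplementary result, with a stated method for EQ-5D missing after repair or dropout. On its own this does not cure the deferral problem.

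Items 1 to 3 are wording plus a modest analysis of repair dates and follow-up that the trial already records. Item 4 needs a small model, and only if avoidance is to be claimed. Treatment and visits do not change. The downside is a headline figure that looks less favourable.

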2. STUDY PLAN AND PROCEDURES

2.1 Study design

The MAAAGI-trial is a population-based multi-center, prospective, parallel group, randomized, open label trial with blinded outcome assessment to assess if metformin up to 2g daily over a five-year period will reduce AAA growth in patients who do not have diabetes.

Patients will be recruited from a cohort of patients with diagnosed AAA at the following seven Swedish sites; 1) Uppsala University hospital, Uppsala, 2), Skåne University hospital, Malmö, 3) Gävle county hospital, Gävle, 4) Västerås county hospital, Västerås. 5) Karlstad county hospital, Karlstad 6) Falun county hospital, Falun, and 7) Umeå University Hospital, Umeå.

The patients should have a maximum aortic diameter of 30-49mm for men and 30-44mm for women, not have diabetes and be expected to tolerate metformin.

A total of 500 patients with AAA will be included in the study, 250 in each study arm. Patients will be randomised to metformin or standard care in a 1:1 ratio.

The patients are scheduled for one enrolment visit, eight study visits and ten phone contacts for those randomized to metformin (three to support titration of study drug) and seven phone contacts for those randomized to standard care. The study visits will take place at the vascular laboratory at the respective surgical departments for clinical examination and blood sampling and at the CT units at the radiology departments where CT-imaging will be performed.

After a run in phase to support titration of metformin, visits and phone contacts are scheduled to alternate every three months until 24 months and twice yearly thereafter. CT imaging and AAA US will be performed at baseline, 24 months and end of study, as well as if necessary according to clinical routine. Study drug will start at baseline and continue through completion.

End of study is defined as 1) study completion at 60 months, or 2) discontinuation from study before that for any reason, for example due to AAA repair or patients will.

When all patients have completed the 24-month follow-up (including imaging) an interim analysis will be performed to assess for efficacy and safety; if there is no trend towards a positive effect or signs of a harmful effect of metformin, the study will be stopped at this phase.

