4.2 Withdrawal from study

Patients may be discontinued from the study at any time, at the discretion of the investigator.

Patients are free to discontinue their participation in the study at any time for any reason.

Patients who discontinue from the study should always be asked about the reason(s) for the discontinuation (and informed about their right not to disclose their reason for doing so) and the presence of any adverse events (AEs). If possible, they should always be seen and assessed by an investigator and asked to perform completion outcome measures, including CT, US and QoL questionnaires. A pre-operative CT may be used for follow up should indication to operate the aorta arise. Adverse events should be followed up.

Study treatment should be stopped in the following cases: development of diabetes, persistent renal failure with GFR<45ml/min, severely deteriorating health, aortic surgery or onset of exclusion criteria.

If the study medication is stopped, patients will be asked to remain in the study and follow the other procedures according to the protocol. All randomised patients remain in the group they were originally allocated to for the purpose of intention-to-treat (ITT) analyses.

Patients who discontinue the study will not be replaced.

Sponsor has to be informed if a patient is withdrawn by any reason before study end. The "End of study" form must be filled out by the investigator and the reason should be stated.

The study number will not be reused if a patient is withdrawn.

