5.1.2 Imaging

At baseline, 24 months and completion, the aorta will be examined by non-contrast enhanced CT with 1 mm slices or thinner from the jugulum to the groins.

At enrolment, 24 months and completion the abdominal aorta will be examined by US. The assessment of abdominal aortic diameter with US will be done by the local US technician, using the standardized technique measuring the largest anterior-posterior diameter from leading edge to leading edge perpendicular to the blood flow in the aneurysm. Inclusion criteria will be based on US determined diameter.

If a subject withdraws from the study due to operative need of the aorta, the preoperative CT will be used for analysis in the study. The assessment of aortic diameter on CT will be done using outer edge to outer edge perpendicular to blood flow. Volumetric AAA analysis of CT images will be performed using manual drawing of the vessel wall contours in axial slices of the entire abdominal aortic as well as semiautomatic measures in 3mensio, Pie Medical, Maastricht. Analysis will start at the slice just below the most distal renal artery excluding accessory renal arteries and end at the slice just above the aortic bifurcation. Measures of perivascular adipose tissue will be made adjacent to the aorta.

All CT assessment (diameter and volume) will be done at a core lab at the Department of Radiology, Uppsala university hospital, Uppsala. The CT identification is the four digits enrolment code. The reviewer will be blinded regarding treatment allocation.

CT images will also be reviewed by local radiologists according to GCP at respective hospital. Accidental findings of unrelated pathology on the CT scan will be dealt with as appropriate by investigator at respective site.

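### Section 8.3 does not say how a pre-operative CT enters the primary ANCOVA or over what interval its growth is annualised; two of the possible readings shrink a true effect

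*Combined protocol and SAP*

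**What the plan says.** **Passages that point to leaving repaired patients out.** Section 8.3 names growth at 60 months as the dependent variable of the ANCOVA, with treatment and baseline AAA as covariates. On missing data it says "The primary analyses will be performed among patients with a measured value at the specific time point". It lists AAA repair among the drop-out reasons for which a sensitivity analysis imputes the worst possible value.

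**Passages that point to keeping them in.**
- Section 2.1: "CT imaging and AAA US will be performed at baseline, 24 months and end of study", where end of study includes "discontinuation from study before that for any reason, for example due to AAA repair or patients will".
- Section 5.1.2: if a patient withdraws because the aorta needs surgery, "the preoperative CT will be used for analysis in the study". Section 4.2 is softer: "A pre-operative CT may be used for follow up should indication to operate the aorta arise".
- Section 8.1 makes ITT the main analysis, asks only for one post-dose efficacy observation, and requires a 60-month measure only for the per-protocol set.
- Sections 8.2.1 and 8.3 express growth per year, although 8.2.1 names only the 24- and 60-month CTs.

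**Follow-up after repair.** Section 2.1 gives repair as an example of leaving the study. Section 4.2 lists "severely deteriorating health, aortic surgery or onset of exclusion criteria" among the reasons to stop treatment, and adds: "If the study medication is stopped, patients will be asked to remain in the study and follow the other procedures according to the protocol".

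**The concern.** Repair is triggered by diameter: 55 mm in section 1.2.2, and 55 mm for men and 50 mm for women in section 1.1. A patient without a 60-month diameter because of repair is therefore usually one whose aneurysm grew fast. If metformin slows growth, more such patients are in the control arm. Leaving them out lowers the control mean more than the metformin mean.

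Including the pre-operative scan does not settle the matter by itself. A change that took two years is a very different rate when divided by two than when divided by five, and the plan does not say which applies.

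At stake is the between-group difference with its 95% confidence interval, which is the trial's main result. With no rule, the choice is made once data exist, in an open-label trial analysed by its own investigators (sections 2.1 and 8).

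**Working it through.** **Inputs from the plan.** Control growth 3 mm/year, SD 2.17, 30% reduction, CT SD 10-15% larger (8.4); entry 30-49 mm for men and 30-44 mm for women (3.1); repair threshold 55 mm (1.2.2).
- Effect: 0.30 × 3 = 0.90 mm/year, so 3.0 versus 2.1.
- Largest SD: 2.17 × 1.15 = 2.50.

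**The plan's own figure.** n per arm = 2(1.96 + 0.84)² × 2.17² / 0.90² = 91.3, so 92 per arm and 184 in total. This agrees with 8.4.

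**One patient (illustrative values).** Entry 43 mm, growth 6 mm/year: 55 mm is reached after 12/6 = 2 years.
- Elapsed time: 12/2 = 6 mm/year.
- Five years: 12/5 = 2.4 mm/year.
- 60-month-only: not in the analysis.

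The same patient growing 0.9 slower (5.1 mm/year) reaches 55 mm after 12/5.1 = 2.35 years. Elapsed time gives 5.1, but five years gives 2.4 again. With a fixed five-year denominator, patients repaired in either case contribute no treatment difference.

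**One entry diameter, by formula.** Take entry at 40 mm and normal growth with SD 2.17. The threshold is reached by 60 months if growth is at least (55 − 40)/5 = 3 mm/year. With z = (3 − μ)/2.17, P = Φ(z) is the share staying below. Their mean is μ − 2.17φ(z)/P; the mean of the rest is μ + 2.17φ(z)/(1 − P).

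| Arm | μ | P | Mean below | Mean above |
|---|---|---|---|---|
| Control | 3.0 | 0.500 | 1.269 | 4.731 |
| Metformin | 2.1 | 0.661 | 0.898 | 4.442 |

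- 60-month-only, all repaired: 1.269 − 0.898 = **0.37**.
- 60-month-only, half repaired: control (0.500 × 1.269 + 0.250 × 4.731)/0.750 = 2.42; metformin (0.661 × 0.898 + 0.170 × 4.442)/0.830 = 1.62; difference **0.80**.
- Divided by five years, all repaired (each contributes 3 mm/year): control 0.500 × 1.269 + 0.500 × 3 = 2.13; metformin 0.661 × 0.898 + 0.339 × 3 = 1.61; difference **0.52**.
- Divided by five years, half repaired: (0.90 + 0.52)/2 = **0.71**.

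**Simulation over a range of entry diameters.** ANCOVA on treatment and baseline; 150,000 patients per arm per scenario; Monte Carlo SE about 0.01. Assumed, not in the documents:
- entry uniform on 30-50 mm, skewed to small, or centred on 36 or 39 mm;
- growth normal or gamma, SD 2.17 or 2.50 taken as slope SD, and an effect that shifts the mean;
- 1 mm CT error;
- repair at 55 mm or six months later, with uptake independent of growth;
- intervals floored at three months;
- women not modelled separately.

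| Uptake at 55 mm | Controls repaired | 60-month-only | Divided by 5 years | Elapsed time |
|---|---|---|---|---|
| 100% | 24-50% | 0.39-0.63 | 0.50-0.74 | 0.88-0.92 |
| 75% | 18-38% | 0.65-0.75 | 0.61-0.79 | 0.88-0.92 |
| 50% | 12-25% | 0.77-0.85 | 0.70-0.82 | 0.88-0.92 |
| 20% | 5-10% | 0.86-0.90 | 0.82-0.88 | 0.88-0.92 |

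**What moves these figures.**
- *Smaller true slope SD.* An observed SD includes measurement error. With slope SD 1.2, 60-month-only gives 0.54-0.66 at 100% uptake and 0.80-0.87 at 50%.
- *Proportional effect.* If metformin multiplies each patient's growth by 0.7, with normal growth (SD 2.17) and full uptake, 60-month-only falls to about zero.
- *Slower growth* (2.0 versus 1.4, true 0.60). 60-month-only gives 0.32-0.48 at 100% uptake and 0.50-0.56 at 50%.
- *Accelerating growth* (slope rising from 0.5 to 1.5 times its mean). Elapsed time falls to 0.73-0.85 at 100% uptake and 0.81-0.88 at 50%, against 0.40-0.67 and 0.76-0.84 for 60-month-only.

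**The case against.** The strongest reply is that sections 2.1, 5.1.2, 8.1 and 8.2.1, read together, already bring the repaired patient's scan into the main analysis, and that a rate in mm/year is naturally taken over elapsed time. The worst-value imputation would then apply only where no usable CT exists. This reading is reasonable, and on it no exclusion bias arises. A reader might infer that the plan will drop repaired patients; the documents do not establish that. What stands is that 8.3, the section an analyst will follow, does not state the joint reading, and no section gives the denominator.

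Second, 8.3 expects repairs to be few, and the bias is then small. That is correct as far as it goes, but the expectation sits poorly with 8.4: at 3 mm/year the average control grows 15 mm in five years, so one entering at 40 mm reaches 55 mm.

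Third, 8.3 plans multiple imputation and worst-value imputation. These may reveal the problem but leave the primary estimate unchanged.

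Fourth, the wording conflicts are minor. *May* in 4.2 concerns follow-up and *will* in 5.1.2 concerns analysis, so the two can be read together. Section 5.1.2 is conditional on withdrawal, which allows for patients who stop treatment but stay.

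**Conclusion.** The point holds as a gap in specification that can bias the primary estimate. The gap is certain. Its effect is conditional on the reading taken and on inputs the documents do not give, above all the share of patients reaching the threshold who are repaired. Of a true 0.90 mm/year, the literal or five-year reading leaves about 0.4-0.7 at full uptake, 0.7-0.85 at half and 0.82-0.90 at one fifth. These figures take the observed SD as slope SD and the effect as a shift in mean growth. Elapsed time gives about 0.9 if growth is roughly linear.

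Three stronger conclusions are not supported.
- *False positives.* With no effect, the 60-month-only estimate stayed within 0.02 of zero and two-sided rejection was 4-7% in 1,000 replicates, so there is no clear inflation.
- *Inadequate power throughout.* At 250 per arm with no other loss and normal growth, 60-month-only power is 48-84% at full uptake but 91-99% at half; with gamma growth it is 96% or more.
- *An equally affected interim.* At 24 months the estimate is 0.74-0.93 at full uptake and 0.84-0.92 at half.

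This should be fixed before the data are analysed.

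**What to change.** In section 8.3:
1. Define the primary outcome as the diameter on the last CT before repair, or on the 60-month CT, minus the baseline CT diameter, divided by the actual years between the two scans. Apply the same rule to early end-of-study CTs where they are obtained.
2. Analyse it in the planned ANCOVA, unweighted. Weights proportional to interval length bring the shrinkage back (0.74-0.85 at full uptake).
3. Fix in advance a minimum interval and what happens below it.
4. State that a CT of a repaired aorta does not count as AAA growth. Section 4.2 could otherwise produce a 60-month value of that kind.
5. Limit worst-value imputation for repair to patients with no usable pre-operative CT.
6. Keep the measured-at-60-months ANCOVA as a sensitivity analysis.

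As minor wording, reconcile 4.2 with 5.1.2 on use of the pre-operative CT, and 2.1 with 4.2 on whether repaired patients remain in follow-up.

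The cost is an amendment to the outcome definition and one sensitivity analysis; the scans are already provided for. The downsides are real. Short intervals give noisier rates. Pre-operative CTs may be acquired differently from the non-contrast study CT. Exit scans depend on feasibility ("If possible, they should always be seen and assessed by an investigator and asked to perform completion outcome measures, including CT"). The rule also assumes roughly linear growth.
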